7.1. Eligibility criteria

7.1.1. Inclusion criteria

Inclusion criteria for those with early psychosis:

- -Age 18-40 (inclusive) at time of eligibility assessment (this age range has been selected in view of typical demographics, and greater chance of secondary psychosis or long-term medication effects above this age range).
- -Able to understand written and spoken English

- -Meets one or more criteria for Ultra High Risk for psychosis groups as assessed by the CAARMS or SIPS, SOFAS and FIGS)
- -Meets criteria for early/first episode psychosis (meet ICD-10 criteria for a diagnosis of schizophrenia and related psychoses (ICD-10 code F20, F22, F25, F28, F29) and within three years of first diagnosis of psychotic disorder at the time of eligibility assessment

Inclusion criteria for those with Parkinson's disease:

- -Age 18-80 (inclusive)
- -Formal diagnosis of idiopathic Parkinson's disease
- -Able to understand written and spoken English
- -Hoehn and Yahr Parkinson's grade 1 4

7.1.2. Exclusion criteria

All participants:

- -Lack of capacity/inability to consent.
- -Significant neurological or psychiatric comorbidity other than psychosis/at risk mental state (e.g. significant mood disorder, nervous system disorders such as stroke, traumatic brain injury).
- Current or lifetime diagnosis of antisocial personality disorder, autism or other neurodevelopmental disorder.
- -Significant risk to self or other people, as determined by their clinical team.
- -Detained under mental health act
- History of alcohol or substance use disorder (abuse/dependence) within six months prior to eligibility assessment (nicotine and caffeine dependence are not exclusionary).
- -Significant upper limb motor impairment (i.e. that would impair squeezing a handheld force-meter or clicking a mouse/button).
- -Significant wrist injuries, carpal tunnel syndrome, or musculoskeletal problems that would cause discomfort in squeezing tasks.
- -Bed-bound or unable to attend University for in-person study

7.2. Sampling

7.2.1. Size of sample

Around 100 participants with Parkinson's disease, and around 100 participants with or at high risk of developing psychosis will be recruited. As there are no existing studies employing the same or similar task, sample sizes have been estimated based on previous related work. A previous analysis¹⁷ by Brysbaert and colleagues estimated that a properly powered reaction time experiment with repeated measures analysed with linear mixed effect models should have at least 1,600 observations per condition (e.g., 40 participants, 40 stimuli), which assumes an effect size between Cohen's d = 0.4 and d = 0.5. Given the experiment contains a total of four experimental conditions (two vs three options, easy vs difficult choice difficulty), 50 participants performing 160 trials would be sufficiently-powered. Another study by Saleh et al.¹⁹ analysed reaction time data and fitted a drift diffusion model to 82 participants with cerebral small vessel disease performing an effort-based decision-making task, including those suffering with apathy. They found a significant correlation between computationally-derived parameters and apathy scores, suggesting that their study of 82 participants performing 180 trials was sufficiently powered. Accounting for a smaller number of (160) trials, 92 participants would be necessary to achieve a similarly-powered study.

For the interview-based study, an estimated sample size of ~10 individuals (~5 with Parkinson's disease and 5 with or at high risk or psychosis) should enable a diverse range of insight while balancing feasibility.

7.2.2. Sampling technique

Convenience sampling will be employed. As all participants will perform the same experiment, there is no rationale for randomisation or group allocation. For the interview-based study, judgement sampling on the basis of performance in the first experiment will guide participant selection. As the experiment principally aims to investigate motivation symptoms, participants with high levels of apathy or negative symptoms, particularly those with exaggerated distractor effects or effort-discounting on the behavioural task, will be preferentially selected for interview.

7.3. Recruitment

7.3.1. Sample identification

Participants with Parkinson's disease:

Potential participants with Parkinson's disease will be identified primarily via charities such as Parkinson's UK or University-held registries of people who have previously expressed interest in participating in research and have consented to be contacted about future research, and therefore for the most part will not rely on NHS resources for participant identification or conduct. For a number of participants, however, an NHS provider may act as a Participant Identification Centre. In this case, potential participants may be identified by their usual clinical team (consultant neurologist or geriatrician or Parkinson's disease specialist nurse, from personal knowledge of potentially eligible patients or database) and approached either in person (e.g. in a clinic) or via written correspondence (letter or email). Capacity to consent will be assessed by their clinical team. Clinicians will inform patients that members of the research team (including Chief Investigator and Primary Investigator who exist outside the direct healthcare team but have contracts with the NHS trust) will confirm eligibility (i.e. diagnosis of idiopathic Parkinson's disease, no exclusion criteria) and will be responsible for the conduct of the study. If seeing patients face-to-face, clinicians may provide some basic verbal information about the study in person (e.g. a study on motivation, duration, payment) and confirm whether they may be interested in participating. Consent to be contacted will be documented in clinical notes. If they are interested, they will either be provided with an information sheet (or link to an information sheet) or be contacted by research staff later via phone or email, who will provide a Participant Information Sheet. Otherwise, potential participants will receive a letter advertising the study and containing the Participant Information Sheet. In both cases, interested participants will be asked to contact the research team. After contacting the research team, potential participants will be provided with a short screening questionnaire to determine eligibility (Microsoft forms page under UoB account or over the telephone). If deemed eligible for the study, an experimental slot will be arranged by a member of the study team. Those people identified via non-NHS sources (e.g. charities) will receive a letter/email or see an advert about the study and will be encouraged to get in contact if interested. Respondents to the advert will receive a link to the information sheet, or will be contacted by research staff via phone or email and provided with a Participant Information Sheet. If they are interested in participating, they will then complete a short screening questionnaire, after which they may be scheduled a study slot.

Participants with or at high risk of psychosis

Potentially eligible participants with early psychosis will be identified either:

 by members of their usual clinical team (consultant psychiatrist or Early Intervention in Psychosis Service team care coordinator - from personal knowledge of potentially eligible patients or from database search.

 via a registry held at the Institute for Mental Health (University of Birmingham) of patients who have previously participated in clinical research (such as PIMS and PRESCIENT studies) and have agreed to be contacted about other research opportunities.

For the first group, capacity to consent will be assessed by the clinical team (consultant Psychiatrist, care coordinator or community psychiatric nurse). Potential participants will be approached either in person (e.g. in a clinic) or via written correspondence (letter or email). If approached in person, members of the clinical team will provide some basic verbal information about the research study and will either provide a Participant Information Sheet or seek verbal consent from participants to be contacted by a researcher who will provide a Participant Information Sheet (via post, email, or link to online information). Consent to be contacted will be documented in clinical notes. Otherwise, potentially eligible participants will be sent a study advertisement letter or email, advertising the study and containing the Participant Information sheet. Clinicians will inform them that members of the research team (including Chief Investigator and Primary Investigator who exist outside the direct healthcare team but have contracts with the NHS trust) will confirm eligibility (i.e. meets inclusion and exclusion criteria) and will be responsible for the conduct of the study. In both instances, participants will be asked to contact a member of the research team (JT - via email) if they are interested in participating in the study. Researchers will then ask participants to complete an eligibility questionnaire, either /Microsoft forms (using UoB account) or over the telephone. If eligible for the study, an experimental slot will be arranged by a member of the study team.

For the second group, researchers will contact participants directly via a study advertisement letter or email, advertising the study and containing the Participant Information sheet. Participants will be asked to contact a member of the research team (JT - via email) if they are interested in participating in the study. Researchers will then send ask participants to complete an eligibility questionnaire via, Microsoft forms (using UoB account) or over the telephone. If eligible for the study, an experimental slot will be arranged by a member of the study team.

Family/friends

It is likely that family members, friends or carers may take an active role in encouraging potential participants to participate in the research. While they will not be considered participants in the behavioural study or interview study, they may wish to be present for these sessions in a supportive capacity. Interviews will focus on individuals' personal motivation symptoms, and while it is possible that family members/carers may provide some commentary on individual patient's symptoms, only comments emanating from participants will be used in the analysis.

7.3.2. Consent

For participants identified via NHS Participant Identification Centres (PICs), potentially eligible patients will be first approached by clinical team (or, if applicable, CRN staff) working within clinical teams, either face-to-face or by a letter or email sent on behalf of the clinical team. Participants will confirm their interest by providing contact details, either via email or via a link to a Microsoft forms page (using JT's UoB account). If these individuals consent to be contacted by the research team, the research team will then take over all correspondence. If participants agree to be contacted, participants will be sent a Participant Information Sheet. They will be encouraged to contact the research team if they have any questions, and to discuss participation with their friends and families. If they express an interest in taking part, they will next complete a screening questionnaire to determine eligibility. They will complete this screening questionnaire via Microsoft forms (using JT's UoB Microsoft account), which will be linked to their unique identifier, or via telephone. This will be completed through implied consent. JT or other investigators will confirm eligibility. If eligible, an experimental slot will be arranged by a member of the study team. Full consent for the experiment will be taken by the experimenter at the beginning of this experimental session (if completing an online interview, an online consent form will be provided). Participants will have already been sent an information sheet and encouraged to ask questions prior to the session, but the key information and ethical issues will be explained verbally before participants are asked to fill the consent form. Capacity will be assessed at the time of this consent process by JT, a neurology doctor with experience in performing capacity assessments. Participants will again have the opportunity to ask questions. The same consent process will apply during any in-person

attendance (for example, during a second experimental session in people with Parkinson's disease, or for the qualitative interview in a subset of participants). For those conducting an interview online, the consent process will be identical to as that in person, although participants will complete an electronic consent form via email. They will have previously received a copy of the Participant Information Sheet via their preferred method (post, email or online copy).

Reimbursement

Participants completing the behavioural task will be reimbursed at a base rate of £25 per session, with a performance-based bonus payment of up to £10 per session. Participants participating in the interview will receive £25 for their participation. Participants will also be reimbursed for travel expenses (excluding taxi fares) including car parking if applicable.

8. Storage and analysis of human tissue

N/A

9. Safety reporting

The risk of adverse events is deemed to be low. Any accidents or injuries occurring during the study will be managed in line with University policy, with input from the Sponsor.

10. Ethical and regulatory considerations

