4.2. Outcome

Evidence-accumulation (computational) models will be fitted to behavioural data to further understand the dynamics of decision-making. It may be that certain apathy dimensions may correlate with specific computationally-derived parameters – for instance, the behavioural activation dimension may correlate with higher thresholds in effort-based task (greater caution), while the cognitive dimension may correspond to slower drift rates or lower response thresholds. These parameters may show dissociation in effort-avoiding and reward-maximising subtasks.

5. Design and methods of data collection and data analysis

Summary

The design will be a mixed quantitative/qualitative analysis. Quantitative data will be in the form of a computer-based decision-making task and questionnaire measures, primarily of apathy and negative symptoms. Qualitative data will take the form of semi-structured interview in a subset of participants.

Design

Those with or at high risk of psychosis will perform one in-person session, while those with Parkinson's disease will complete two counterbalanced sessions - once having taken their usual dopamine-modulating medication, and once having omitted this medication the same morning. These sessions will take place on separate days within 2 weeks of one another. If participants with Parkinson's disease feel unable to omit their medication, or do not take medication for Parkinson's disease, only a single session will be arranged. Testing will take place in person at the University of Birmingham.

At the point of recruitment, participants will receive a unique identifier. Pseudonymisation will be performed by [name] (JT). The database linking personal data to ID numbers will be maintained by JT in a single, password-encrypted Excel file on the University server. All datafiles generated will only refer to participants with their unique ID numbers.

[figure not shown]
Participants will receive a payment of £25 for participation in a session, plus up to £10 additional payment based on their performance in the task (i.e. up to £35 for a single session).

Behavioural study and questionnaires

(estimated time 1h 30 to 2h 5, depending on clinical group/session number)

- All participants will first receive a brief explanation of the study and provide written consent (~5 minutes).

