1.1. Risk category

Tick the appropriate box below to indicate trial type:

×	Τ\	YPE A		ТҮРЕ В		ТҮРЕ С
	Comparable to the risk of standard medical care		Higher than the risk of standard medical care		1	kedly higher than the risk of dard medical care
			1	rials involving medicinal products icensed in any EU Member State if: such products are used for a new indication, substantial dosage modifications are made for the licensed indication, or	For n	TIMPs: Trial involving a medicinal product not licensed in any EU Member State. on-CTIMPs Project involving a new surgery technique, a new radiotherapy technique or a new diagnostic technique
For	Pro obs	and/or guidelines. CTIMPs: jects involving skin prick tests, ervational measures or quality ife assessments.	For no	suspected. Trials involving medicinal products not licensed in any EU Member State of the active substance is part of a medicinal product licensed in the EU. On-CTIMPs: Projects involving radiotherapy dose modifications or a new combinations of non-IMP treatment (e.g. surgery and radiotherapy).		

Justification for risk category:

Guidance

List the intervention(s) and briefly justify the overall risk category selected (Type A, B or C). Consider the following:

- a. Phase of development
- b. Study population healthy subjects or patients?
- c. Is the intervention licensed?
- d. Is the intervention being used outside of its licensed indication?
- e. Has the dosage regimen/route/surgical procedure/fractionation been modified? If so what are the implications of any modifications for participants?
- f. What is the safety profile of the intervention(s).
 - i. What are the known/anticipated safety issues? Are they all addressed within normal clinical practice (standard care)?
 - ii. Anticipated risks/other effects based on pre-clinical data or knowledge of class of intervention?
 - iii. Is the duration of use compatible with previous experience? Is there a potential risk of dosing errors?
 - iv. May concomitant medication increase the risk i.e. interactions?
 - v. Is there any published evidence particularly for Type A trials intending to submit via the MHRA Notifications Scheme, or to support a risk category different to that indicated above?

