The intervention involves withholding a single dose of a symptomatic (i.e. non-disease-modifying) medication for Parkinson's disease. This will have no adverse effects on the disease trajectory but may temporarily worsen Parkinsonian symptoms such as slowness, stiffness and tremor.

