1.2. Risks related to the intervention

List below the key risks related to the intervention(s) and how these risks will be minimised. Consider all significant project-specific medical events. Examples are provided in red italic text. Add or delete rows as required.

Intervention	Body system/hazard	Mitigation/activity (including frequency)	Comments (including impact and likelihood where applicable)
		-Participants will be adequately informed of risks of withholding medication and provide informed consent.	
Withhold		-Participants will be offered a choice of whether to withhold medication for the study.	
single dose of dopaminergic medication (includes	-Worsening of tremor -Worsening of	-Participants will withhold a single dose of medication and take the scheduled next dose without delay	
levodopa, dopamine agonists, monoamine oxidase	-Worsening of slowness -Increased risk of falls	-Participants and researchers will ensure risk associated with trips and falls are mitigated. This includes ensuring participants are accompanied and have	
inhibitors)		adequate transport arrangements, clarifying usual level of mobility and ensuring appropriate walking or mobility	
		aids are provided, ensuring testing rooms are accessible by wheelchair, signposting toilets and assessing participant's needs	

frequently, ensuring no hazards in the environment that could lead to falls.

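### Parkinson's participants whose first session is unmedicated omit their dose before giving informed consent, although the risk assessment lists that consent as a safeguard for the omission

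*Protocol*

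**What the plan says.** **Consent and capacity.** Section 5 (Behavioural study and questionnaires) opens the session with consent: "All participants will first receive a brief explanation of the study and provide written consent". Section 7.3.2 agrees: "Full consent for the experiment will be taken by the experimenter at the beginning of this experimental session". It assigns a capacity assessment to the study doctor at that same step. The project flow chart also shows consent as the first item of session 1.

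**Medication.** Section 5 (Design) gives Parkinson's participants one session on their usual medication and one "once having omitted this medication the same morning". Section 10.1 starts sessions between 0900 and 1030, puts the delay to the dose at about 3 to 6 hours, and has the dose taken straight after the session. The flow chart and section 5 counterbalance the order, and section 13.4 (table 2.2) describes it as randomised. For people who cannot omit medication or take none, "only a single session will be arranged".

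**Risk assessment.** Section 13.4 describes the intervention this way: "The intervention involves withholding a single dose of a symptomatic (i.e. non-disease-modifying) medication". The category ticked is Type A, "Comparable to the risk of standard medical care". Table 1.2 lists as mitigations that "Participants will be adequately informed of risks of withholding medication and provide informed consent" and, as a separate item, that "Participants will be offered a choice of whether to withhold medication for the study".

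**The concern.** A safeguard protects only if it comes before the exposure it is meant to cover. For participants tested unmedicated first, the omission requested by the study precedes the informed consent that section 13.4 relies on. It also precedes the study doctor's capacity check. Section 10.1 accepts that the unmedicated state may make walking harder and raise the risk of falls, and eligibility runs to Hoehn and Yahr grade 4. The journey to the site is made in that state. Someone who declines at the session, or is found there to lack capacity, has already delayed a dose for research.

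The timing of the falls counselling is less clear. Section 10.1 and table 2.2 of section 13.4 place it within the consent process, a term that section 7.3.2 uses for the step at the session. On that reading the counselling also comes too late, but the text is ambiguous and this is not put forward as a contradiction.

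The trial's estimates, power and error rates are not affected.

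**Working it through.** The protocol gives no figure to reproduce. The check is the order of events, one timing calculation and a count.

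**Order of events when session 1 is unmedicated**
1. Information sheet sent, questions invited, screening completed under implied consent, session booked (7.3.2).
2. Usual morning dose omitted on the day (5, 10.1).
3. Travel to the site.
4. Session starts between 0900 and 1030: verbal explanation, study doctor's capacity check, written consent (5, 7.3.2).
5. Task and questionnaires, then the delayed dose (10.1).

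Steps 2 and 3 precede step 4. Nothing in the protocol describes an earlier consent step for the behavioural sessions; electronic consent by email is offered only for online interviews (7.3.2). When session 1 is medicated, consent at that session precedes the omission, so nobody in that order is affected.

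**Time from usual dose to consent**
- Inputs: delay of 3 to 6 h (10.1); Parkinson's session 1 of about 2 h 5 min (flow chart, section 5); dose taken straight after the session (10.1).
- Formula: gap = delay − session length.
- Shortest: 3 h − 2 h 5 min = 55 min.
- Longest: 6 h − 2 h 5 min = 3 h 55 min.
- Rounded to about 1 to 4 h, since the protocol gives the delay only approximately. In clock time the usual dose lies between 0505 (0900 − 3 h 55 min) and 0935 (1030 − 55 min).

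**Number affected**
- Formula: participants doing both sessions × 1/2, with 1:1 order assumed.
- The target is about 100 Parkinson's participants (7.2.1). The proportion doing both sessions is not stated, so a range is assumed.

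| Do both sessions (assumed) | Unmedicated first |
|---|---|
| 100 | 50 |
| 80 | 40 |
| 60 | 30 |

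**The case against.** The strongest reply is that these participants omit the dose informed and by choice, and only the signature and formal capacity check come late. Several points support it:

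- The information sheet is sent beforehand with an invitation to ask questions. It is not in the file and may well cover omission and falls.
- Table 1.2 of section 13.4 offers a choice about withholding, and the single-session rule in section 5 implies that omission is raised before booking.
- Accompaniment and transport have to be arranged before arrival, which suggests some earlier contact about the unmedicated state.
- Lack of capacity is an exclusion criterion and screening precedes booking. For people identified through NHS centres, section 7.3.1 has the clinical team assess capacity.
- Harm is limited. Someone who declines on arrival can take the dose then, after about 1 to 4 h instead of the planned 3 to 6 h.

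Most of this stands and limits the weight of the point, but it does not change the order. Receiving a sheet is not giving consent: section 7.3.2 still has the key information explained verbally before the form is signed. Section 13.4 lists choice and informed consent as separate mitigations, so one does not stand in for the other. Section 7.3.1 names charities and registries as the main Parkinson's route, and describes no capacity assessment before the session for people who come that way.

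**Conclusion.** The concern holds. Followed as written, the protocol places its own intervention before the informed consent listed as a mitigation for it, and before the study doctor's capacity check, for every Parkinson's participant whose first session is unmedicated. That is up to about 50 people, or 30 to 40 if 60% to 80% do both sessions. These counts rest on 1:1 order and on assumed proportions. The interval of about 1 to 4 h rests on the stated delay and session length, and on the dose being taken straight after the session.

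The sequence itself is certain from the text; the timing of the falls counselling is not. The weight is modest: one delayed symptomatic dose in a study rated Type A, with practical precautions planned. It should be corrected because consent is a basic protection and the remedy is cheap.

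**What to change.** In section 7.3.2, require that any Parkinson's participant scheduled unmedicated first gives documented consent before a dose is omitted. The emailed electronic form already used for online interviews would serve. Pair it with a short conversation, by telephone or in person, covering the omission, falls risk, accompaniment, transport and a capacity check. Reconfirm consent at each session. State in sections 10.1 and 13.4 that the counselling takes place at this contact.

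Session order, counterbalancing and the medication instruction stay as they are. The order must already be known before session 1, because the participant has to be told whether to omit that morning's dose. Making session 1 always the medicated one would also solve the problem, but it would lose the counterbalancing.

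The cost is a protocol amendment, which may need ethics committee review before it takes effect (10.2), and one short extra contact per affected participant. At an assumed 10 to 15 minutes each:
- 50 participants: 50 × 10 min = 8.3 h, to 50 × 15 min = 12.5 h.
- 30 participants: 30 × 10 min = 5 h, to 30 × 15 min = 7.5 h.
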